5.2.5 Impaired Hepatic Function

Table 5-C.

Please see Table 5-C below for the appropriate dose adjustments based on total bilirubin and AST. In cases of obstruction of the biliary duct by a tumor mass, a biliary drainage stent may be placed prior to chemotherapy. Values must be within protocol eligibility at treatment initiation.

Table 5-C:Total Bilirubin with Appropriate DoDose Adjustments		Doxorubicin and	d Vinblastii	ıe		
	Drug ¹	Total Bilirubin:	Total Bilirubin:	Total Bilirubin:	Total	

Drug ¹	Total Bilirubin:	Total Bilirubin:	Total Bilirubin:	Total
	< 1.5	1.5 – 3	3.1 – 3.5	Bilirubin:
	AST: < 60	AST: 60 - 180	AST: > 180	> 3.5
Doxorubicin	Administer	Administer	Administer	Safety Not
	100%	50%	25%	Established
Vinblastine	Administer	Administer	Administer	Safety Not
	100%	50%	25%	Established

If participants are receiving atazanavir, please use only the direct bilirubin as an indicator 1. for dose reduction of doxorubicin or vinblastine, following the dose reduction guidance identically as for total bilirubin

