- 7. **PFTs** with volumes, spirometry, DLCO and room air pulse oximetry. Patients will be required to obtain a pulmonary function test, despite the exclusion of bleomycin. The DLCO adjusted for hemoglobin must be greater than 70% predicted to enter the study and to continue with brentuximab vedotin.

- 8. **Bone marrow biopsy** for histology and determination of percent bone marrow involvement. If bone marrow involvement by lymphoma has already been documented after bone marrow biopsy performed more than 6 weeks prior to registration, the biopsy does not have to be repeated.
- 9. Central pathology review for confirmation of histology of lymphoma specimen: Biopsy material at diagnosis will be sent to confirm HL and histologic subtype. (See Appendix 20.1 and 20.7 for the acceptable specimens required for central review and for handling instructions).

All specimens will be reviewed by a panel of pathologists and must be submitted within 30 days of study enrollment. Patients who are found not to have HIV-HL will be withdrawn from the study

- 10. Laboratory tests, including:
 - CBC with differential and sedimentation rate (within 2 weeks prior to patient registration).
 - Serum chemistries: electrolytes (Na, K, Cl, bicarbonate, Ca, Mg, and phosphorus), glucose, blood urea nitrogen (BUN), creatinine, total bilirubin, alkaline phosphatase (ALP), LDH, total protein, albumin, AST and ALT (within 2 weeks prior to patient registration).
 - CD4 and CD8 cell count.
 - HIV-1 RNA viral load assessed by any approved viral load assay at the local laboratory. This must be performed within 21 days prior to Cycle 1, Day 1. (The HIV viral load assay must detect at minimum viremia >200 copies/mL to be consistent with the DHHS HIV treatment guidelines).
 - Assessment for Hepatitis C antibody, Hepatitis B core antibody, Hepatitis B surface antigen (HBsAg), and Hepatitis B surface antibody.
 - Serum pregnancy test for women of childbearing potential (within 7 days prior to Cycle 1 chemotherapy). (See Section 13.1.1 under pregnancy and breastfeeding for guidelines on the use of pregnancy category D medications, which includes brentuximab vedotin and dacarbazine.)
- 11. Blood collection for biological analyses (cf. Appendix 20.7) after signature of informed consents for biological and genetic studies.

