9.4 Evaluation during treatment

- 1. Update **medical history** prior to each cycle of chemotherapy. History to include concomitant medication changes and any signs and symptoms. Reportable adverse events must be recorded in AdvantageEDC. To be performed within 48 hours prior to or on first day of each cycle.
- 2. **Physical examination** prior to each cycle of chemotherapy. Examination to include performance status (Appendix 20.5). All subjects will be evaluated for clinical response by physical examination prior to receiving treatment on each cycle. The exam should occur within 2 days prior to the start of each cycle but may occur on Day 1 of cycle. Disease measurable by physical examination will be recorded in two dimensions if possible. To be performed within 48 hours prior to or on first day of each cycle.
- 3. **FDG-PET/CT**. Combined FDG-PET/CT or FDG-PET + CT scans with and without IV contrast are required for this study. If a patient has an allergy to IV contrast, a CT scan without contrast will be permitted.
 - Restaging evaluation by a full body FDG-PET/CT within Day 22-28 of Cycle 2 (i.e., 7-13 days after the Cycle 2 Day 15 doses of AVD-BV). If the CT portion of the PET/CT is a non-contrast CT, an additional CT scan with and without contrast must be obtained. Tumor measurements and SUVs must be

documented. A neck CT must be included if palpable neck nodes were present at baseline and a diagnostic CT is being performed.

- As the false positive rate of FDG-PET scans may be higher in the HIV population, a biopsy of an unexpected FDG-PET avid lesion is recommended but remains at the discretion of the investigator.
- 4. **PFT** with volumes, spirometry, DLCLO, and room air pulse oximetry will be performed after every 2 cycles, on day 1 of cycles 3 and 5, within 7 days of cycle initiation. The DLCO adjusted for hemoglobin must be greater than 70% predicted to continue with therapy.
- 5. Neuropathy evaluation by completing the FACT/GOG-neurotoxicity **questionnaire** at the beginning of each cycle. To be performed once within 48 hours prior to or on first day of each cycle (Appendix 20.6).
- 6. **CBC** with differential within 48 hours of day 1 and 15 of each cycle. Results of CBC must be known prior to treatment.

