- 7. Serum chemistries within 48 hours of day 1 and 15 of each cycle: electrolytes (Na, K, Cl, bicarbonate, Ca, Mg, and phosphorus), glucose, blood urea nitrogen (BUN), creatinine, total bilirubin, alkaline phosphatase (ALP), LDH, total protein, albumin, AST and ALT. Results do not need to be known prior to treatment unless clinically indicated.
- 8. **CD4/CD8** count will be performed within 48 hours of cycle 2 and cycle 5 day 1 along with the CBC evaluation.
- 9. **HIV-1 RNA viral load**, assessed by any approved viral load assay at the local laboratory. This will be performed within 48 hours of cycle 2 and cycle 5 day 1 along with the CBC evaluation. (The HIV viral load assay must detect at minimum viremia >200 copies/mL to be consistent with the DHHS HIV treatment guidelines).

For patients with undetectable HIV viral at baseline: If the viral load rises above 200 copies per mL, HIV resistance testing will be required. Both viral load and resistance testing information must be shared in real time with the primary HIV provider if different from the protocol investigator. (The HIV viral load assay must detect at minimum viremia >200 copies/mL to be consistent with the DHHS HIV treatment guidelines).

10. **Serum pregnancy test** for women of childbearing potential will be performed per institutional guidelines during the study.

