Impaired Hepatic Function	All patients with direct bilirubin ≤ 2 x the upper limit of normal (ULN) will receive a full initial dose of doxorubicin and vinblastine. If the direct bilirubin rises to ≥ 2 x ULN (but ≤ 5 x ULN), the doxorubicin and vinblastine doses must be reduced by 50% of last dose received to avoid undue hepatic toxicity. Full doses should be given once the direct bilirubin is ≤ 2 x ULN. If the direct bilirubin rises to ≥ 5 x ULN, doxorubicin and vinblastine should be discontinued for that cycle. If the direct bilirubin has not recovered to ≤ 2 x ULN by the time the next cycle is due, then remove patient from protocol treatment. In cases of obstruction of the biliary duct by a tumor mass, a biliary drainage stent should be placed prior to chemotherapy. Values must be within protocol eligibility at treatment initiation. Direct Bilirubin with appropriate Doxorubicin and Vinblastine Dose Adjustments ≤ 2 x ULN = 100% of last dose received
	> 2 - 5 x ULN = 50% of last dose received
	> 5 x ULN = discontinue (i.e., do not administer)
Neuropathy	Once brentuximab vedotin has been discontinued, patients experiencing Grade 3 vinblastine-neuropathy (e.g., obstipation, weakness) will have the dose of vinblastine reduced by 50% for all further cycles of AVD. Patients experiencing Grade 4 vinblastine neuropathy will have this drug omitted from all future cycles of AVD.
Pulmonary Toxicity	Every 2 cycles PFT will be performed. The DLCO adjusted for hemoglobin must be greater than 70% to continue with brentuximab vedotin.
Weight	If a subject's weight has changed more than 10% from baseline or the prior dose, the new BSA must be used on the next cycle. For a weight change of 10% or less, doses may be adjusted according to the BSA or remain the same in conjunction with institutional guidelines.

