13.0 CRITERIA FOR PREMATURE DISCONTINUATION OF THE STUDY

13.1 Premature withdrawal from trial intervention

After enrollment, subjects will be permanently withdrawn from study treatment for any of the following reasons. In the event of withdrawal from treatment, the reason for study treatment removal and the date the subject was removed must be documented in the Off Protocol Treatment Form in AdvantageEDCSM. See Section 9.6 on evaluations to be performed at early discontinuation of therapy.

- 1. Participants who experience a delay of over 7 days in cycle 1 will be removed from the study. For subsequent cycles, if two sequential doses of AVD + BV or AVD alone are held due to unresolved toxicity, leading to a treatment delay of an additional 2 weeks (i.e., 4 weeks between doses), the participant will be taken off protocol therapy. The participant will be followed for survival and may resume AVD treatment off study.
- 2. Severe toxicities as outlined in Section 10.6.1.
- 3. Progressive lymphoma at any time while on study.
- 4. Voluntary withdrawal.
- 5. The investigator has the right to remove subjects from study for clinical reasons which he or she believes to be life threatening or resulting in significant morbidity to the subject.
- 6. Any subject who develops HBV reactivation or acute Hepatitis B as defined by the reappearance of a previously suppressed hepatitis B surface antigen, a positive IgM hepatitis B core antibody, and a positive viral load. Any patient with Hepatitis B or C who has worsening liver function as defined by Section 10.6.2 will also be removed from study.
- 7. Any subject who on repeat PFT is found to have a DLCO when corrected for anemia less than 70%.
- 8. Subjects who become pregnant or breast-feed.
- 9. Subjects with progressive disease at the end of cycle 2 will be removed from study treatment, while patients with stable disease may be removed from the study treatment at the discretion of the local responsible investigator. Progressive or stable disease defined at cycle 2 will be based by CT criteria only, as FDG-PET has yet to be validated in HIV-associated HL.
- 10. If found by central pathology review to not have the diagnosis of HL.

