Central pathology review	Х																	
Blood sampling for biological studies	Х																	
CBC with diff Results must be known prior to treatment Sedimentation rate (only at baseline)	X (W-2)	X (h-48)	X (h-48)	X (h-48)	X (h-48)		X (h-48)	X (h-48)	X (h-48)	X (h-48)	X (h-48)	X (h-48)	X (h-48)	X (h-48)	X	Х	х	Х

	Treatment (W-2) Must be completed within 2 weeks prior to patient registration (D-7) To be performed within 7 days prior to first day of cycle (D-21) To be performed within 21 days prior to Cycle 1, Day 1 (D-28) To be performed no more than 28 days before enrollment. (H-48) To be performed within 48 hours of day 1 and 15 of every cycle.													ay of cycle	Follow-up			
Date (weeks or months)	Eligibility (Baseline) 6 weeks before C1D1	C1D1	C1D15	C2D1	C2D15	C2D22 -28	C3D1	C3D15	C4D1	C4D15	C5D1	C5D1 5	C6D1	C6D15	End of treatment 6 -8 w after C6D15	Early Treatment Discontinuatio n 1 m after discontinuation	Every 3 m 2 y (+/-7d)	Every 6 m 3 y (+/-7d)
Serum chemistries: electrolytes (Na, K, Cl, bicarbonate, Ca, Mg, phosphorus), glucose, BUN, creatinine, total bilirubin, alkaline phosphatase (ALP), LDH, total protein, albumin, AST and ALT	X (W-2)	X (h-48)	X (h-48)	X (h-48)	X (h-48)		X (h-48)	Х	Х	Х	Х							
 CD4/CD8 cell count (e) to be performed at study completion and every 3 months for one year (f) Do not repeat if done within 1 month from removal from treatment. 	x			X (h-48)							X (h-48)				X(e)	X(f)		
HIV-1 RNA viral load (g) to be performed at study completion and every 3 months for one year (h) Do not repeat if done within 1 month from removal from treatment.	X (D-21)			X (h-48)							X (h-48)				X (g)	X(h)		
Hepatitis C antibody, Hepatitis B core antibody, Hepatitis B surface antigen (HBsAg), and Hepatitis B surface antibody	X																	

	(W-2) N	Treatment (W-2) Must be completed within 2 weeks prior to patient registration (D-7) To be performed within 7 days prior to first day of cycle (D-21) To be performed within 21 days prior to Cycle 1, Day 1 (D-28) To be performed no more than 28 days before enrollment.													le	Follow-up			
	(H-48) To be performed within 48 hours of day 1 and 15 of every cycle.																		
Date (weeks or months)	Eligibility (Baseline) 6 weeks before C1D1	C1D1	C1D15	C2D1	C2D15	C2D22 -28	C3D1	C3D15	C4D1	C4D15	C5D1	C5D1 5	C6D1	C6D15	End of treatment 6 -8 w after C6D15	Ear Treat Discont n 1 m disconti	ly ment inuatio after nuation	Every 3 m 2 y (+/-7d)	Every 6 m 3 y (+/-7d)

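### French doxorubicin and vinblastine hepatic dosing depends on direct bilirubin, which no French schedule collects, and both protocols let Day 1/15 chemistry go unread before the dose it sets

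*Combined protocol and SAP*

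**What the plan says.** **French dose rule.** Section 10.6.2, Impaired Hepatic Function, gives three bands under "Direct Bilirubin with appropriate Doxorubicin and Vinblastine Dose Adjustments": full dose up to 2 x ULN, half dose above 2 and up to 5 x ULN, and no dose above 5 x ULN. The middle band is mandatory: "the doxorubicin and vinblastine doses must be reduced by 50% of last dose received to avoid undue hepatic toxicity". Failure to recover to 2 x ULN by the next cycle means removal from treatment. Neither total bilirubin nor AST triggers a change. Section 13.1, item 6, relies on the same section: "Any patient with Hepatitis B or C who has worsening liver function as defined by Section 10.6.2 will also be removed from study".

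**French schedule.** The baseline list in 9.3 reads "creatinine, total bilirubin, alkaline phosphatase (ALP), LDH, total protein, albumin, AST and ALT (within 2 weeks prior to patient registration". The flow chart in 21.2 reads "glucose, BUN, creatinine, total bilirubin, alkaline phosphatase (ALP), LDH, total protein, albumin, AST and ALT", and 9.4 item 7 lists the same analytes for Days 1 and 15.

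**AMC.** Table 5-C in section 5.2.5 doses on total bilirubin and AST. Its footnote makes an exception: "If participants are receiving atazanavir, please use only the direct bilirubin as an indicator". Appendix XIII allows atazanavir with caution. The chemistry lists in 8.1.12.2, 8.2.6 and Appendix I give total bilirubin only.

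**Timing.** AMC 8.2.6 and French 9.4 item 7 carry the same sentence on Day 1/15 chemistry: "Results do not need to be known prior to treatment unless clinically indicated". The blood count is treated differently. French 9.4 item 6 says "Results of CBC must be known prior to treatment", and AMC 8.2.5 and Appendix I footnote H impose the same condition. Footnote G, which covers AMC chemistry, does not.

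**The concern.** There are two mismatches between a dose rule and the schedule that should feed it.

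- **The value is not collected.** A French site that performs every scheduled test still lacks the one number its hepatic dose rule uses. The same is true of an AMC site treating a participant on atazanavir.
- **The value need not be seen.** In both protocols, a site may give doxorubicin and vinblastine before reading the chemistry that determines how much to give.

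The exposure is foreseeable. Hepatotoxicity is a listed brentuximab vedotin risk, the dacarbazine text mentions hepatic toxicity and liver necrosis, and participants with hepatitis C or treated hepatitis B may enrol. At stake is overdosing of two cytotoxic drugs during a liver abnormality, together with inconsistent application of the removal rules.

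**Working it through.** No statistical figure is involved. The check sets the dose rules beside the schedules and then works out the dose difference per affected administration.

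**Step 1: is the dose-setting value scheduled?** Only lists that can feed a dose are counted. Follow-up and early-discontinuation lists are left out because nothing is dosed from them.

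| Participants | Value that sets the dose | Lists checked | Lists naming it |
|---|---|---|---|
| French | Direct bilirubin | 9.3, 9.4 item 7, 21.2 | 0 of 3 |
| AMC on atazanavir | Direct bilirubin | 8.1.12.2, 8.2.6, Appendix I | 0 of 3 |
| AMC, all others | Total bilirubin and AST | 8.1.12.2, 8.2.6, Appendix I | 3 of 3 |

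Across both protocols, direct bilirubin is in 0 of 6 lists and total bilirubin in 6 of 6.

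**Step 2: must the value be known first?** No, in either protocol, for Day 1 and Day 15 chemistry. Both hepatic sections require values within eligibility at treatment initiation, so the timing point is claimed only for later doses: 6 cycles x 2 doses = 12 planned, less the first = 11. History and examination, which could reveal a clinical reason to wait, are scheduled before each cycle only. The 6 Day 15 doses have neither scheduled.

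**Step 3: dose difference per affected administration.** Full doses are 25 mg/m² doxorubicin and 6 mg/m² vinblastine. Required dose = full dose x band percentage. Excess = full dose − required dose.

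| Band | Required doxorubicin / vinblastine (mg/m²) | Ratio if full dose is given | Excess (mg/m²) |
|---|---|---|---|
| 50% (both protocols) | 12.5 / 3 | 25/12.5 = 6/3 = 2 | 12.5 / 3 |
| 25% (AMC) | 6.25 / 1.5 | 25/6.25 = 6/1.5 = 4 | 18.75 / 4.5 |
| Above 5 x ULN (French) | 0 / 0 | not defined | 25 / 6 |

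For total bilirubin above 3.5, AMC Table 5-C gives no dose and says safety has not been established.

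**Step 4: how long can it persist?** AMC samples once per dose, and doses are 14 days apart. A total bilirubin or AST result missed at one dose is normally back by the next, so about one dose is affected per new rise. That limit does not hold for French participants, or for AMC participants on atazanavir, because no scheduled result ever shows direct bilirubin. Their only scheduled prompt is a raised total bilirubin or liver enzyme.

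**Step 5: is total bilirubin an adequate prompt?** Not always. Both protocols admit participants with total bilirubin up to 3.5 mg/dL attributed to antiretrovirals, provided direct bilirubin and transaminases meet stated limits. French criterion 9 also admits Gilbert's syndrome with total bilirubin up to 3 x ULN. In these participants total bilirubin is already raised at entry, so a high value later says less.

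**The case against.** The strongest opposing case is that the rule supplies its own remedy. A mandatory dose rule cannot be followed without its input, so a site is bound to obtain direct bilirubin. The AMC footnote tells sites outright to use it. Direct bilirubin is part of total bilirubin, which is scheduled with the liver enzymes before every dose, and the eligibility criteria (AMC 3.1.9, French criterion 9) already follow a raised total with the direct fraction. The timing waiver has a clinical-indication exception, and product information or institutional guidelines also apply (AMC 7.1.1 and 7.1.2, French 10.4). The worst cases need a jump from the full-dose band to the most severe band within 14 days with nothing clinical to prompt a check. France plans only 20 of the 51 participants, and there may be no atazanavir users at all.

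Much of this stands as a limit on likelihood. Sites may order the test, the dose rules stay binding, and the most extreme rises are the least likely to go unnoticed. The AMC direct-bilirubin gap is narrow. The AMC footnotes for chemistry and blood count differ in substance only in the requirement that results be known, since neither bars same-day sampling.

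None of it closes the gap. The eligibility use of direct bilirubin is conditional and applies at entry. No text makes direct bilirubin a scheduled test during treatment, and the timing waiver leaves the dose-setting result unread unless someone already suspects a problem.

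**Conclusion.** The concern holds and should be fixed. In the French protocol, the sole hepatic dosing value is missing from all three chemistry lists that could supply it. In AMC, the same omission affects atazanavir users only. In both, the waiver on chemistry results conflicts with dose rules that depend on those results.

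The dose ratios of 2 and 4, and the full French dose where none is due, are conditional. They assume a first, unsuspected rise, a preceding full dose, and a site that follows the schedule and waiver as written without ordering extra tests. They are not estimates of harm. The documents give neither the frequency of abnormal liver values nor the number of atazanavir users, so no expected count is offered. This is a patient-safety inconsistency; the estimate of two-year progression-free survival is unaffected.

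**What to change.** 1. Add direct bilirubin to the serum chemistry in French 9.3, 9.4 item 7 and the 21.2 flow chart.
2. In AMC 8.1.12.2, 8.2.6 and Appendix I, add it for participants on atazanavir or with raised total bilirubin.
3. Amend AMC 8.2.6 and French 9.4 item 7 so that the dose-setting values are known before doxorubicin and vinblastine are given. For AMC these are total bilirubin and AST, or direct bilirubin on atazanavir. For the French protocol it is direct bilirubin. The waiver can stay for the other analytes.

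No change to the dose bands is proposed. The cost is amendment wording, one extra result from blood already drawn, and a short wait on dosing days, as is already required for the blood count.

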5.2.6 Neuropathy

Once brentuximab vedotin has been discontinued, participants experiencing Grade 3 vinblastine-neuropathy (e.g., obstipation, weakness) may continue the study receiving AVD with dose adjustments in vinblastine as clinically necessary, based on the level of neuropathy on the day of treatment. Participants experiencing Grade 4 vinblastine neuropathy will have this drug omitted from all future cycles of AVD.

5.2.7 If a participant's weight has changed more than 10% from baseline or the prior dose, the new BSA must be used on the next cycle. For a weight change of 10% or less, doses may be adjusted according to the BSA or remain the same in conjunction with institutional guidelines.

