	Grade 2	 Treatment is to be delayed until neuropathy improves to Grade 1 or baseline Brentuximab vedotin will be reduced by one dose level for subsequent treatments once peripheral neuropathy returns to baseline or returns to grade 1. Patients who experience a delay of over 7 days in cycle 1 will be removed from the study. For subsequent cycles, if two sequential doses of brentuximab vedotin are held due to unresolved toxicity, leading to a treatment delay of an additional 2 weeks (i.e., 4 weeks between doses), participant will discontinue brentuximab vedotin. Participants will have the option to discontinue protocol therapy or continue study with AVD with dose adjustments in vinblastine as clinically necessary based on the level of neuropathy on the day of treatment as per standard label/summary product characteristics.
	Grade 3	 Treatment is to be delayed until neuropathy improves to Grade 1 or baseline. Brentuximab vedotin will be reduced by one dose level for subsequent treatments once a peripheral neuropathy returns to baseline or returns to grade 1. Patients who develop grade 3 neuropathy after dose reduction will have to discontinue brentuximab vedotin. Subjects will have the option to be taken off protocol or continue study with AVD with dose adjustments as clinically necessary. Patients who experience a delay of over 7 days in cycle 1 will be removed from the study. For subsequent cycles, if two sequential doses of brentuximab vedotin are held due to unresolved toxicity, leading to a treatment delay of an additional 2 weeks (i.e., 4 weeks between doses), the participant will discontinue protocol therapy or continue study with AVD with dose adjustments in vinblastine as clinically necessary, based on the level of neuropathy on the day of treatment as per standard label/Summary product characteristics.
	Grade 4	Discontinue brentuximab vedotin.
Neutropenia occurring on the day of treatment	Grade 1-2	Continue at same dose level.

Event	CTCAE.v4.0 Grade	Action to be Taken

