- 11. If the subject has had two cycles of AVD + brentuximab vedotin and develops recurrent Grade 3 peripheral neuropathy despite dose reductions of brentuximab vedotin and vinblastine, the subject may continue the study receiving AVD with dose adjustments in vinblastine as clinically necessary, keeping in mind to maintain the dose and schedule as in standard therapy, or may be removed from protocol treatment. This decision will be at the discretion of the investigator.

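### For Grade 3 neuropathy after brentuximab vedotin has stopped, the French protocol gives a fixed vinblastine cut in one section and discretion in others, and the AMC protocol has only discretion

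*Combined protocol and SAP*

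**What the plan says.** **French (LYSARC) protocol**
- Section 10.6.2, Neuropathy row. The trigger is Grade 3 neuropathy attributed to vinblastine in someone already off brentuximab vedotin. The consequence is that these patients "will have the dose of vinblastine reduced by 50% for all further cycles of AVD".
- Section 10.6.1.2, Peripheral Neuropathy rows. A participant who has two consecutive brentuximab vedotin doses held may go on with AVD. The Grade 2 row then provides for "dose adjustments in vinblastine as clinically necessary based on the level of neuropathy on the day of treatment", and the Grade 3 row says the same apart from a comma. For Grade 3 neuropathy after a brentuximab vedotin dose reduction, the Grade 3 row says: "Subjects will have the option to be taken off protocol or continue study with AVD with dose adjustments as clinically necessary".
- Section 13.1, item 11. This covers a participant who "develops recurrent Grade 3 peripheral neuropathy despite dose reductions of brentuximab vedotin and vinblastine". AVD may continue with "dose adjustments in vinblastine as clinically necessary, keeping in mind to maintain the dose and schedule as in standard therapy", at the investigator's discretion.

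**AMC protocol**
- Section 5.2.6, the counterpart of French 10.6.2, opens with the same trigger. Its Grade 3 instruction is that such a person "may continue the study receiving AVD with dose adjustments in vinblastine as clinically necessary, based on the level of neuropathy on the day of treatment". It contains no 50% figure.
- Section 4.6.10 and Table 5-A carry discretionary wording like that of French 13.1 item 11 and 10.6.1.2.

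French Section 16.0 states that French and US data are pooled for analysis. French Section 7.0 plans 20 of the 51 participants in France.

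**The concern.** A mandatory cut that lasts for every remaining cycle and a dose chosen visit by visit are different rules. Once a participant is on AVD alone with Grade 3 neuropathy, a French investigator can find both in the same protocol, and a US investigator finds only the second.

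Both protocols name the overlapping neuropathy of brentuximab vedotin and vinblastine as something to be managed (AMC 2.4.5, French 5.7). Neurotoxicity is a secondary objective (AMC 1.2.7, French 6.2). One stopping condition concerns Grade 3 neurotoxicity that lasts more than four weeks (AMC 4.7.1, French 13.4). How long neuropathy lasts after brentuximab vedotin stops may depend on how much vinblastine is still given, although the documents do not say so. The statistical sections pool the two countries and do not plan a summary of vinblastine dose, so a reader of the pooled neurotoxicity table could not tell which rule had been applied.

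**Working it through.** The plan gives no figure of its own on this point. The check is a comparison of texts, followed by an illustration of size.

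**Step 1. Do the passages reach the same participant?** Take a participant whose brentuximab vedotin has stopped, who continues AVD and who has Grade 3 neuropathy.
- French 10.6.2 applies if the neuropathy is attributed to vinblastine. It gives obstipation and weakness as examples but no criterion for separating vinblastine neuropathy from neuropathy left by brentuximab vedotin.
- The French 10.6.1.2 Grade 3 row governs the decision to stop brentuximab vedotin and also the vinblastine dose in the AVD that follows.
- French 13.1 item 11 covers recurrent Grade 3 neuropathy in a participant who goes on with AVD.
- AMC 5.2.6 has the same trigger as French 10.6.2. Both omit vinblastine for Grade 4, so only the Grade 3 rule differs.

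**Step 2. Can all be followed together?** French 10.6.2 fixes the size of the cut (50%) and its duration (all further AVD cycles). It has no provision for going back up, although the severe-infection row of the same table leaves re-escalation to the treating physician. The other passages fix neither size nor duration. They agree with 10.6.2 only if the investigator happens to choose 50% at every remaining dose.

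**Step 3. Possible size.** Inputs from French 10.1: vinblastine 6 mg/m² on days 1 and 15 for 6 cycles.
- Planned: 2 × 6 = 12 doses, and 12 × 6 = 72 mg/m².
- If *k* full doses precede the cut, the fixed rule gives 6*k* + 3(12 − *k*) = 36 + 3*k* mg/m².
- Cut from dose 5 (*k* = 4): 36 + 12 = 48 mg/m²; 48/72 = 67%.
- Cut from dose 11 (*k* = 10): 36 + 30 = 66 mg/m²; 66/72 = 92%.
- Discretionary wording: no figure is set, and up to 72 mg/m² is permitted.

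Measured against no cut at all, the gap is 72 − 48 = 24 mg/m² (33% of plan) in the first case and 72 − 66 = 6 mg/m² (8%) in the second.

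The onset time is an assumption. Dose 5 is the earliest case if the sentence in French 10.6.1.5 and AMC 5.1.3, which ends study therapy for participants unable to receive four brentuximab vedotin doses, applies generally. If it does not, a cut from dose 3 would give 36 + 6 = 42 mg/m² (58%). All cases assume that every dose is given and that vinblastine was not cut earlier for another reason.

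**Step 4. How many participants?** The ceiling is 20 French participants. The documents give no Grade 3 neuropathy rate for this regimen in this population. Taking the 10% used in the stopping rule as an assumption, 20 × 0.10 = 2, and only those who are on AVD alone would face the conflict.

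**The case against.** The best defence is that the sections have different jobs. French 10.6.1.2 modifies brentuximab vedotin for peripheral neuropathy, while 10.6.2 addresses neuropathy attributed to vinblastine once brentuximab vedotin is gone. On that reading the more specific rule governs and nothing conflicts. This stands in part: the passages do not collide in every case. They still collide for a participant on AVD alone with Grade 3 neuropathy, because 10.6.1.2 and 13.1 item 11 also set the vinblastine dose in that period. I found no statement of precedence, and precedence within the French protocol would not remove the difference from AMC 5.2.6.

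A second defence is that discretion permits a 50% cut, and that French 10.6.1.2 refers the adjustment to the product label. The label is not reproduced, so the documents cannot show whether the rules coincide. It is therefore right to say only that exposure *can* differ. Each participant is also treated under one country's protocol.

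A third defence is that few participants are involved. That stands.

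A reader might also infer that the trigger in AMC 4.6.10 and French 13.1 item 11, recurrence despite reductions of both drugs, can never occur because vinblastine reduction for neuropathy opens only after brentuximab vedotin stops. The documents do not support this. Neither AMC 5.2.6 nor French 10.6.2 says only then. Vinblastine may already have been reduced for severe infection or hepatic impairment, or after brentuximab vedotin stopped and before the neuropathy recurred.

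**Conclusion.** The inconsistency is real and narrow. French 10.6.2 cannot be followed together with French 10.6.1.2 and 13.1 item 11 for a participant on AVD alone with Grade 3 neuropathy, unless the investigator's judgement happens to match the fixed cut. It also differs from AMC 5.2.6.

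Under the assumed onset times, the fixed rule gives 67% to 92% of planned vinblastine, against anything up to 100% under discretion. The number affected is probably small.

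Three stronger readings should be avoided:
- That several French sections tie the dose to the neuropathy level on the day. Only 10.6.1.2 does. Item 11 of 13.1 is discretionary and leans towards keeping the standard dose and schedule.
- That exposure must differ. The documents show only that it can.
- That the pooled PFS estimate is compromised. Nothing in the documents shows a material effect on PFS from so few participants.

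What is at stake is a usable instruction for investigators and an interpretable neurotoxicity summary. This review takes no position on which vinblastine rule is right.

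**What to change.** The sponsor and the clinical leads should reconcile French 10.6.2 with French 10.6.1.2 and 13.1 item 11, and all three with AMC 5.2.6, Table 5-A and 4.6.10, so that one vinblastine rule applies to all participants. The choice of rule is theirs.

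The analysis should report the vinblastine dose given after neuropathy onset, by country, beside the neurotoxicity results. For participants who have already completed treatment, the report should state which rule was followed.

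The cost is a wording amendment and one descriptive table, assuming the vinblastine doses given are already recorded. No visits or tests are added, and the sample size and primary analysis do not change.
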